2.1. Design Overview

This is a multi-period crossover study where each participant will receive four 2-week treatment periods of TJ-68/placebo. We plan to randomize a total of 26 participants, with 13 randomized to Treatment Sequence A: TJ-68-Placebo-Placebo-TJ-68, and another 13 to Treatment Sequence B: Placebo-TJ-68-TJ-68-Placebo, with a 1-week washout period between treatment periods. That is, each participant will receive TJ-68 and Placebo each in two separate treatment periods. Assuming 15% attrition, we expect to have 22 evaluable participants. Balanced randomization of the two alternating treatment sequences will eliminate linear trend in the primary analysis.

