2.3. Analysis Populations and Missing Data

All efficacy analyses will be performed using the modified intent-to-treat (mITT) population. The mITT population consists of all randomized participants with outcomes evaluated in at least two (out of four) post-randomization periods with at least one period in TJ-68 and one in Placebo.

As sensitivity analyses, we will also perform efficacy analyses in the completers only, that is, participants with outcome evaluated in all 4 treatment periods.

Safety analyses will be performed as treated.

Missing data patterns will be compared by treatment sequence as well as by the treatment periods. While the primary analyses will be performed in the mITT population defined above, we will perform sensitivity analyses using imputed data sets under different imputation approaches:

- (A) Mean imputations: Missing data within a treatment period will be imputed using averages from other data points within the same treatment period. If data in the entire treatment period is missing, the observations from the previous period will be carried forward.
- (B) Worst-outcome imputations: All missing data will be imputed using the worst values observed in a treatment group.

3. Primary Efficacy Analysis

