3.3. Sample Size Consideration

We aim to enroll 22 evaluable participants equally to the two alternating TJ-68/Placebo sequences over the four treatment periods, i.e., each participant will have 4 observations. Under the LME model, assuming a within-participant standard deviation of 1.4 based on our pilot data, this sample size will yield about 85% power to detect a 1-point shift on MCS VAS. Assuming 15% attrition, we will plan to enroll a total of 22 participants.

4. Safety Analysis

Adverse events (AE), including the presence of hypokalemia, will be summarized by treatment per participant. The AE will be attributed to the period in which it is observed. AE rate by treatment will be summarized using proportion and 95% confidence intervals and will be compared using McNemar test. Longitudinal AE data will be modeled using generalized linear mixed effect model with a logit link.

5. Secondary Outcome Analyses

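### If an adverse event occurs only on TJ-68, no analysis planned in section 4 gives a usable interval for the excess risk

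*Combined protocol and SAP*

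**What the plan says.** Section 4 of the SAP sets out three layers of AE analysis.

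- A descriptive summary: "Adverse events (AE), including the presence of hypokalemia, will be summarized by treatment per participant". Hypokalemia is the only AE named. Timing is settled by "The AE will be attributed to the period in which it is observed".
- A comparison: "AE rate by treatment will be summarized using proportion and 95% confidence intervals and will be compared using McNemar test".
- A model: "Longitudinal AE data will be modeled using generalized linear mixed effect model with a logit link".

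Section 2.3 adds "Safety analyses will be performed as treated". Section 2.1 says "We plan to randomize a total of 26 participants" and that "each participant will receive TJ-68 and Placebo each in two separate treatment periods". Section 3.3 counts 22 evaluable participants.

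Section 4 does not say how the mixed model is estimated or tested, what happens if one treatment has no events, whether hypokalemia is modelled alone or pooled with other AEs, which form of McNemar's test is used, or which result leads. It plans no interval for the difference between treatments.

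**The concern.** A logit model estimates the treatment effect as a log odds ratio. When one treatment has no events and the other has some, the data are separated: the likelihood keeps rising as the log odds ratio grows, and no finite maximum exists. Software stops at an arbitrary large value with a very large standard error, so a Wald p-value goes towards 1 however many events occurred on the active treatment.

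A zero count on placebo is plausible for an uncommon event with about 44 to 52 placebo periods. The remaining analyses in section 4 give two one-treatment intervals and a p-value. None of these measures how much TJ-68 raises the risk or how precisely that is known, which is what a reader of a phase 1/2 safety analysis wants for the one event the plan names.

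**Working it through.** Section 4 states no numerical figure to reproduce, so the check uses a constructed example and assumed rates.

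**Inputs.** 22 evaluable participants (section 3.3) or up to 26 as treated (sections 2.1 and 2.3). Two periods per treatment each (section 2.1): 2 × 22 = 44 periods per treatment, or 2 × 26 = 52. Example: 6 participants with one event each on TJ-68 and none on placebo. The example and all event rates are assumptions.

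**Step 1: the model.** The period-level log odds ratio is log(6/38) − log(0/44), which is infinite.

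- Plain logit fit: the software stops at 21.7 with standard error 11,979. Then z = 21.7/11,979 = 0.002 and Wald p = 0.999.
- Random-intercept logit fit by quadrature: with the log odds ratio set to 8, 12 and 16, the negative log-likelihood is 17.5280, 17.5257 and 17.5257, so there is no turning point. The standard errors are 20.7, 153 and 1,130, giving Wald p of 0.70, 0.94 and 0.99. The p-value depends on where the optimiser stops.
- Likelihood-ratio test: the log-likelihood with a treatment effect is 6 ln(6/44) + 38 ln(38/44) = −17.526, and without it 6 ln(6/88) + 82 ln(82/88) = −21.904. Twice the difference is 8.76, p = 0.003.

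The plain-fit Wald p stays at 0.998–0.999 with 3, 6, 11 or 22 affected participants, and with 22 or 26 in the analysis. The zero cell is the cause, not the sample size.

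**Step 2: the other planned analyses, 6 against 0 in 22.**

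- Exact (Clopper-Pearson) intervals: 6/22 = 27.3% (10.7% to 50.2%), and 0/22 with upper limit 1 − 0.025^(1/22) = 15.4%. They overlap, and neither concerns the difference.
- McNemar: exact 2 × 0.5^6 = 0.031; asymptotic 6²/6 = 6.00, p = 0.014; continuity-corrected 5²/6 = 4.17, p = 0.041.

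**Step 3: what stays finite.**

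- Paired risk difference with Tango score interval. With b and c participants affected only on TJ-68 and only on placebo, solve (b − c − nΔ)/√{n[2q + Δ(1 − Δ)]} = ±1.96 for Δ, where q is the placebo-only probability estimated under Δ. At n = 22: 6/22 = 27%, interval 8% to 48%. At n = 26: 6/26 = 23%, interval 7% to 42%.
- Firth-penalised logit fit (clustering ignored, for illustration): odds ratio 15.0, profile-likelihood interval 1.7 to about 2,000, p = 0.011. It is wide, but finite and in line with McNemar's test.

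**Step 4: how often.** Assume independent periods with risk p on placebo and r on TJ-68. With 22 participants, separation has probability (1 − p)^44 × [1 − (1 − r)^44]. Exact McNemar below 0.05 with no placebo events needs at least 6 affected participants (5 against 0 gives 2 × 0.5^5 = 0.0625). Each participant is affected on TJ-68 with probability 1 − (1 − r)²: 0.0975 at r = 5% and 0.19 at r = 10%. The binomial chance of at least 6 of 22 is then 0.016 or 0.228.

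| Placebo risk per period | No events in 44 | Separation, r = 5% / 10% | Separation and exact p < 0.05, r = 5% / 10% |
|---|---|---|---|
| 0.5% | 80% | 72% / 79% | 1.3% / 18% |
| 1% | 64% | 58% / 64% | 1.0% / 15% |
| 2% | 41% | 37% / 41% | 0.7% / 9% |

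With 26 participants, separation runs from 0.98^52 × (1 − 0.95^52) = 0.350 × 0.931 = 33% to 0.995^52 × (1 − 0.90^52) = 0.770 × 0.996 = 77%. The last column depends on sample size: at 26 the chance of at least 6 affected is 0.036 or 0.372, so it runs from 0.350 × 0.036 = 1.3% to 0.770 × 0.372 = 29%.

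**The case against.** A reader might infer that the model would hide the clearest possible safety signal. Section 4 does not support that. The proportions and McNemar's test come before the model and remain defined with no placebo events. In the example the report would show 6/22 against 0/22 with p below 0.05 in all three forms of the test.

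A reader might also infer that the model and McNemar's test would contradict each other whenever TJ-68 causes events that placebo does not. That is too strong. Most separated results have few TJ-68 events, where the exact test is not significant either (3 against 0 gives p = 0.25), so the limit there is power. A conflict with a significant exact test has about a 1–18% chance at 22 participants. It is larger if the asymptotic test is used, since 4 against 0 then suffices (p = 0.046): 7–13% at 5% TJ-68 risk and 26–50% at 10%.

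Three further points stand. The SAP names neither Wald tests nor unpenalised estimation, and a likelihood-ratio test of the same model responds properly. A standard error near 12,000 is a recognisable fitting failure that an analyst is unlikely to read as no effect. And the model is planned for longitudinal AE data in general; if AEs are pooled, a zero placebo count is less likely.

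None of this supplies an interval for the excess risk. Even profiling the unpenalised likelihood leaves the odds ratio without a finite upper limit, and McNemar's test gives only a p-value.

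**Conclusion.** The point holds as a limited gap in the estimation of AE risk. When placebo events are zero, the unpenalised model has no finite odds ratio, its Wald output would be meaningless, and the other planned analyses do not give an interval for the TJ-68 minus placebo difference. The signal itself stays visible.

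It would be wrong to blame the sample of 22: the same failure occurs at 26.

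The failure under separation follows from the model alone. Its likelihood rests on per-period rates that are not in the documents, and on independent periods: about 33–79% for separation over 22 to 26 participants. The harm from an outright conflict between analyses is much less likely than separation if the exact test is used. The change is worth making because it is cheap and the recommended quantities stay finite with a zero cell.

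**What to change.** In section 4:

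- Make the per-participant paired risk difference (TJ-68 minus placebo) with a Tango score 95% interval the leading AE comparison, for hypokalemia on its own as well as for AEs overall.
- Report McNemar's test beside it, and fix one form in advance, exact or mid-p. The choice matters at the margin: 5 against 0 gives 0.0625 exact and 0.0625 − 0.5^5 = 0.031 mid-p.
- Fit the logit mixed model with a penalised likelihood or a weakly informative prior. Report profile-likelihood or posterior intervals in place of Wald tests, and label the model supportive.
- Say how as-treated participants observed on only one treatment are reported, since they cannot enter a paired comparison.

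The cost is a few sentences in the SAP and a few lines of code. No data collection changes. The one statistical downside is that the model odds ratio is shrunk slightly towards no difference; the paired risk difference is not affected.

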5.1. Additional Analyses of MCS

Secondary outcomes based on the MCS include (i) total MCS score, (ii) cramp frequency, severity, or both measured via the Cramp Diary (CD), (iii) MCS Additional Questions, and (iv) VAS of Cramp Pain. These secondary outcomes will be analyzed using LME in the same manner as in the analysis of the primary outcome.

5.2. Other Secondary outcomes

Other secondary outcomes of the study include ALSFRS-R within each treatment period, clinical global impression of changes (CGIC) within each treatment period, quality of life measured via ALSAQ-5 within each treatment period, and goal assessment scale (GAS) within each treatment period. As these outcomes are measured longitudinally, they will be analyzed using LME models.

5.3. Heterogeneity of treatment effects and plasma metabolomics

We will perform exploratory analysis to understand treatment mechanism via heterogeneity of treatment effects. Specifically, plasma metabolomics will be measured longitudinally, and will be included as a longitudinal covariate in the LME models. Its interaction with treatment effects will also be explored.
